9.1. Adverse Events

An adverse event (AE) is defined as any untoward medical occurrence in a patient enrolled into this study regardless of its causal relationship to study drug. Adverse events will be assessed from the time the patient signs the ICF until exit from the study. In addition to patient observations, AEs identified from any study data (eg, laboratory values, physical examination findings, ECG changes) or identified from review of other documents that are relevant to patient safety will be defined as AEs and recorded appropriately. All AEs reported or observed during the study will be recorded on the AE page in the eCRF. Adverse events will be coded using MedDRA (Version 20.1 or higher).

An overall summary of the number and percentage of patients having any treatment emergent adverse event (TEAE), serious TEAE, treatment-related TEAE, treatment-related serious TEAE, TEAE leading to permanent discontinuation of treatment, TEAE leading to study discontinuation, TEAE with outcome death, and TEAE of special interest will be provided by treatment group. All AEs will be listed including the investigator term, the preferred term, start and end dates of the AE, duration (days), severity, drug relationship, action taken, and outcome for all screened patients.

9.1.1. Incidence of Treatment Emergent Adverse Events

A treatment-emergent adverse event (TEAE) is defined as any event not present before exposure to study drug or any event already present that worsens in either intensity or frequency after exposure to study drug. If start date of an AE is missing after imputation, the corresponding AE will be included as TEAE if end date of AE is after the first dose of study drug or the end date is also missing. Imputation for partial AE start dates and end dates can be found in Appendix 13.4.

The number and percentage of patients with at least one TEAE will be summarised by MedDRA system organ class (SOC) and preferred term (PT). At each level of SOC or PT, a patient will be counted only once if the patient reported multiple events.

The above analysis will also be conducted for TEAEs occurred from V0 to V3 and by subgroups as defined in section 4.4.

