6.3.1.6 Exceptions

The hospitalisation due to study-related procedures ie, for scheduled RHC and PEA will not be considered as an SAE for this study.

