7.8.4 Safety Analyses

Safety analysis except by-visit summarisations will be presented in 2 ways, one based on only the assessments during the double blind treatment phase, and another based on the assessments during the whole study.

Adverse events will be summarised by presenting for both treatment groups the number and percentage of patients having any AE, having an AE in each MedDRA primary system organ class, and having each individual AE (preferred term). Additionally, a summary of AEs by preferred term and severity will be performed using the worst severity grade.

All related AEs, AEs with outcome death, AEs leading to permanent discontinuation of treatment, SAEs, and related SAEs will be summarised by percentages and frequencies and listed including the investigator term, the preferred term, start and end dates of the AE, duration (days), severity, drug relationship, action taken, and outcome.

Treatment-related AEs are those rated by the investigator as “definite,” “probable,” or “possible.” In case the relationship is unknown or missing, the worst case will be assumed and the AE will be considered to be drug related.

For laboratory data, the proportion of patients with clinically significant abnormal values as reported by the investigator will be provided by laboratory parameter, dose cohort, and scheduled visit.

For each laboratory parameter, shift tables of baseline categories based on normal ranges (below, within, above) versus categories at each postbaseline scheduled visit and the worst postbaseline value will be provided.

Summary statistics of values and changes from baseline over time will be computed for all safety laboratory parameters.

For vital sign measurements, supine or seated blood pressure and HR (absolute values and change from baseline) will be summarised by dose cohort and scheduled visit.

For ECGs, the proportion of patients with a clinically significant abnormal ECG result will be provided. A summary of shifts in 12-lead ECG abnormalities from baseline will be provided by scheduled visits.

Abnormal physical examination data will be summarised by treatment group and body system with number and percentage of patients.

Previous and concomitant treatments coded using the WHO Drug Dictionary and medical history coded using MedDRA will be summarised by treatment group number and percentage of patients at different coded terms.

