9.1.6. TEAEs Leading to Death

TEAEs with outcome death will be summarised by SOC and PT using the frequency counts and percentages.

All-cause of death during the whole study course will be presented in a listing.

The above analysis will also be conducted for TEAEs occurred from V0 to V3 for overall patients in the Safety set and by subgroups as defined in section 4.4.

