9.5. Physical Examination

A complete physical examination including assessments of the head, eyes, ears, nose, throat, skin, neck (including thyroid), lungs, cardiovascular system, abdomen, lymph nodes, and extremities will be obtained at screening. A physical examination including updates since the screening visit with focus on previously noted abnormalities in organ systems, including skin and hair, will be completed at time points specified in Schedule of Events.

Physical examination data will be summarised by treatment group and body system with number and percentage of patients.

Physical examination results for all patients will be presented in a listing.

10. Interim Analysis

A data safety monitoring board (DSMB) will review unblinded safety data throughout the study and make recommendations as appropriate. Further details are specified in the DSMB charter.

11. Changes in the Planned Analysis

The changes for the statistical analyses from the protocol to this SAP are stated below:

1. The analysis set to be used for perioperative endpoints (Circulatory Arrest Time, Surgery-related Complications, Surgical Evaluation of Specimen, PEA hospital length of stay, PEA ICU length of stay, Time on mechanical ventilation, In-hospital mortality) have been updated to PEA set only, with the consideration that these endpoints are peri-PEA surgery related endpoints and it makes more sense to narrow down the patients to those who have undergone PEA surgery only.
2. The analysis sets to be used for postoperative endpoints (Percent Change in PVR from baseline to Visit 4, Composite clinical endpoint from baseline to Visit 4, NT-proBNP, cardiac output, cardiac index, mRAP, mPAP, PAWP change from baseline to Visit 4, Functional class at Visit 4, All-cause death, Need for PAH-targeted postoperative therapy at Visit 4) have been updated to PEA set and PPS, with the consideration that the endpoints are post-PEA surgery endpoints, and it makes more sense to restrict the analysis to patients who undergone PEA surgery; PPS will be used since those per-protocol patients need to be considered as a complementary analysis set.

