13.1. Schedule of Events

	Visit 0 Pretreatment / Screening	Visit 1 Randomisation & baseline visit	Visit 2 RHC visit (Pre- PEA)	Visit 3 Post-PEA	Visit 4 Follow-up visit incl. RHC
Time frame	Day -89 to 1	Day 1	Day 90+30	Day 96 ^a	Day 276±10
Activity / Observation					
Written informed consent	X				
Inclusion/exclusion criteria review	X	(X) ^b			
Assessment of current tobacco use	X				
Demographic data including height and weight	X				
HIV test	(X) ^b	X			
Medical and treatment history	X	X			
Physical examination including WHO functional class	X	X	X	X	X
Vital sign measurements	X	X	X	X	X
Clinical laboratory assessments (haematology, clinical chemistry, and urinalysis)	(X) ^b	X	X	X	X
NT-proBNP measurement		X	X		X
Haemodynamics incl. PVR, mRAP, mPAP, cardiac index, pulmonary artery wedge pressure measurement	X ^c		X		X
12-lead ECG		X	X		X
Pregnancy test (if applicable) ^d	X	X	X		X
Randomisation/treatment assignment		X			
Administration of double-blind study drugs ^e		X	X		
Provision of patient diary	X				

	Visit 0 Pretreatment / Screening	Visit 1 Randomisation & baseline visit	Visit 2 RHC visit (Pre- PEA)	Visit 3 Post-PEA	Visit 4 Follow-up visit incl. RHC
Time frame	Day -89 to 1	Day 1	Day 90+30	Day 96 ^a	Day 276±10
Activity / Observation					
Perioperative assessment (circulatory arrest time, surgery-related complications)			X ^f		
Surgical evaluation of specimen ^g				X ^g	
Hospital and ICU length of stay				X	
Time on mechanical ventilation				X	
PAH-targeted therapy assessment	X	X	X	X	X
PH-related hospitalisation		X	X	X	X
Adverse event monitoring	X	X	X	X	X
Concomitant medications		X	X	X	X
Return of patient diary				X	
Return of study drug				X	
Telephone call			X ^h		X ⁱ
Patient compliance check (study procedures and study drug)		X	X	X	X

Abbreviations: ECG, electrocardiogram; HIV, human immunodeficiency virus; ICU, intensive care unit; incl., including; mPAP, mean pulmonary arterial pressure; mRAP, mean right atrial pressure; NT-proBNP, N-terminal pro-B-type natriuretic peptide; PAH, pulmonary arterial hypertension; PEA, pulmonary endarterectomy; PH, pulmonary hypertension; PVR, pulmonary vascular resistance; RHC, right heart catheterisation; WHO, World Health Organization

^a The PEA will be conducted by the principal surgeon of the site within a week of RHC.

^b When laboratory analysis results are required/available (see Protocol Section 4.2)

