13.3. Surgery-related complications

Surgery-related complications are defined as the following:

- Bleeding and/or blood loss >1 L in 12 hours
- Airway bleed with need for extracorporeal membrane oxygenation
- Any use of extracorporeal membrane oxygenation for respiratory or haemodynamic support, specified as veno-venous or veno-arterial
- Prolonged ventilation >96 hours
- Need for tracheostomy
- Need for drainage of pericardial effusion
- Neurological complications, ie, stroke, cerebral, subdural bleeding
- Reintubation or noninvasive ventilation for reperfusion response
- Haemoptysis requiring any intervention
- Renal failure requiring dialysis
- Wound infections
- Pneumonia
- Prolonged need for inotropic support (≥ 5 days)

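### The SAP plans no general adverse event tables for the double-blind treatment phase in the overall safety set; its Visit 0 to Visit 3 window reaches past surgery, and the change is not declared

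*SAP*

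**What the plan says.** Protocol 7.8.4 sets two presentations for safety analyses other than by-visit summaries: "one based on only the assessments during the double blind treatment phase, and another based on the assessments during the whole study".

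SAP 9.1.1 specifies a TEAE table with no time limit and then adds: "The above analysis will also be conducted for TEAEs occurred from V0 to V3 and by subgroups as defined in section 4.4". Sections 9.1.2 to 9.1.6 repeat this for relatedness, severity, seriousness, discontinuation and death, and name the population. In 9.1.6, for example: "The above analysis will also be conducted for TEAEs occurred from V0 to V3 for overall patients in the Safety set". The TEAE definition reads "defined as any event not present before exposure to study drug or any event already present that worsens in either intensity or frequency", counted once dosing has begun; no end limit is given.

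A shorter window, Visit 0 to Visit 2, appears in two places: SAP 4.4, for the concomitant-medication subgroups, and SAP 9.1.7, for events of special interest.

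The schedule in SAP 13.1 heads the relevant column "Visit 3 Post-PEA", and Protocol 6.2.15 has the postoperative hospital and ICU stay reported at that visit. Protocol 3.1 and SAP 3.1 both put the last dose on the morning of PEA.

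SAP section 11 begins "The changes for the statistical analyses from the protocol to this SAP are stated below". It lists five numbered changes and a note on the timing of the specimen evaluation. None concerns the adverse event window.

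**The concern.** Safety and tolerability of riociguat is a secondary objective, and every patient who completes treatment goes straight from the last dose into major surgery. A table that runs to the post-surgery visit therefore mixes events on drug with events of the operation.

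Nothing in the definitions keeps the two apart. The only stated exception to serious event reporting is narrow: "The hospitalisation due to study-related procedures ie, for scheduled RHC and PEA will not be considered as an SAE for this study". The 13 items in SAP 13.3, introduced by "Surgery-related complications are defined as the following", are not exempted. SAP 9.1.3 shows severity at the worst grade, so a severe surgical event overrides a milder on-drug event of the same term. Missing relationship is counted as related and missing severity as severe (SAP 9.1.2 and 9.1.3), in the perioperative period as well.

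Two things are at stake. The prespecified tables may blur a difference between arms that belongs to the drug. And if a treatment-phase table is added later, its window would be chosen after unblinding, without having been prespecified.

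**Working it through.** The documents give no figure to reproduce here. The check is a comparison of texts, followed by arithmetic on timing and an illustration of dilution.

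**1. Tables planned in SAP 9.1.1 to 9.1.6.** TEAEs (1), relatedness (1), severity (1), serious and related serious (2), leading to treatment and to study discontinuation (2), fatal (1): 1 + 1 + 1 + 2 + 2 + 1 = 8. Each is planned without a limit and for Visit 0 to Visit 3.

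**2. Windows side by side.**

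| Source | Population | Window |
|---|---|---|
| Protocol 7.8.4 | Safety analyses except by-visit | Treatment phase; whole study |
| SAP 9.1.1–9.1.6 | Overall safety set | Unlimited; Visit 0 to Visit 3 |
| SAP 4.4 | Medication subgroups | Visit 0 to Visit 2 |
| SAP 9.1.7 | Events of special interest | Visit 0 to Visit 2; Visit 0 to Visit 4 |

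For the overall safety set, 0 of the 8 tables is limited to the on-drug, pre-surgery period. The Visit 0 start is harmless, because a TEAE requires exposure. The fault is at the end of the window.

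**3. Where the treatment phase ends.** Protocol 3.1 gives Day 90 for the period and the morning of PEA for the last dose. The withdrawal endpoint (Protocol 7.2, SAP 8.2.6) closes the randomised treatment phase before PEA. None of these extends beyond surgery.

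**4. How far Visit 0 to Visit 3 overruns.** This is not stated. Visit 3 is nominally Day 96 and Visit 4 Day 276; 276 − 96 = 180 days, about the six months after PEA at which Visit 4 is planned. So Day 96 is also about the nominal day of PEA, although the visit is labelled as following it and covers the hospital stay. No cut-off date is given, and patients without a Visit 3 have no stated end.

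**5. What the Visit 0 to Visit 2 cuts miss.** Dosing continues until PEA, up to 7 days after Visit 2.
- Nominal days: (96 − 90)/96 = 6/96 = 6.3% of dosing days.
- Visit 2 on Day 90, PEA 7 days later: 7/97 = 7.2%.
- Visit 2 on Day 120, PEA 7 days later: 7/127 = 5.5%.

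**6. Dilution (illustration only).** Let p1 and p0 be the on-drug event probabilities, and let s be a perioperative probability that is equal in both arms and independent of on-drug events. The probability in an arm becomes 1 − (1 − p)(1 − s), so the risk difference becomes (p1 − p0)(1 − s). The documents give no s.

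| Assumed s | Factor 1 − s | Any-event difference, 92% vs 86% |
|---|---|---|
| 0% | 1.00 | 6.0 points |
| 10% | 0.90 | 5.4 points |
| 30% | 0.70 | 4.2 points |
| 60% | 0.40 | 2.4 points |

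The 92% and 86% are the CHEST-1 rates in Protocol 1.4, borrowed only as an example.

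**The case against.** The best counter-argument is that Visit 0 to Visit 3 is meant as the treatment phase. The SAP has two presentations, as the protocol does. Dosing runs on after Visit 2, so Visit 3 is the first visit boundary that loses no on-drug days, and the overrun may be short. On this reading the fault is a loose end date. The inference is fair, and the SAP never says that it drops the treatment-phase tables. But it does not say that Visit 0 to Visit 3 stands in for them either, and a window that ends at a post-surgery visit still includes surgery.

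Second, pre-surgery tables do exist. Anticoagulation is mandatory, so the anticoagulant subgroups may cover much of the safety set, and if they are split yes/no as in SAP 7.1, the two halves would add up to whole-set counts to Visit 2. That depends on a split that SAP 4.4 does not state, and those cuts stop before the last dose. Sections 9.1.1 to 9.1.6 also name the same subgroups next to Visit 0 to Visit 3, so it is unclear which window governs them.

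Third, the harm is uneven. This stands. Surgical events rated unrelated stay out of the related rows and the related-serious table. TEAEs leading to treatment discontinuation, and terms that surgery does not cause, are largely unaffected. Events of special interest have their own cut to Visit 2, and in-hospital deaths are tabulated separately (SAP 8.3).

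Fourth, the dilution factors rest on assumed values and on equal risk in both arms, while the effect of riociguat on safety during PEA is itself under study. That also stands: they show direction and range, not an estimate.

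**Conclusion.** The concern holds. Protocol 7.8.4 promises a treatment-phase presentation; for the overall safety set the SAP specifies none among its 8 general TEAE tables and offers a window that extends beyond surgery. Section 11 is silent, although it declares another departure from the same protocol section (the laboratory table) and another change of observation period (the composite endpoint).

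The finding rests on the text alone. The size of the distortion is unknown. The factors of 0.90 to 0.40 assume s between 10% and 60%, equal in both arms and independent of on-drug events, and in tables by preferred term s would differ for each term. All adverse events are listed with dates and all analyses are exploratory, so the defect lies in the prespecified tables and their declaration, not in lost data. It should be corrected before unblinding.

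**What to change.** - In SAP 9.1.1 to 9.1.7, add a treatment-phase window for the overall safety set, defined by dates: first dose to the start of PEA, or to last dose (with any lag prespecified) for patients without PEA. Present it beside the whole-study tables.
- Keep Visit 0 to Visit 3 only as an additional table, labelled as including the perioperative period, since safety during PEA is its own objective. Give it an end date, including for patients with no Visit 3.
- State one window for the medication subgroups, the same in 4.4 and 9.1.
- List any remaining departure from Protocol 7.8.4 in section 11.

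The cost is SAP wording and one extra table set, plus two rules. Events starting on the day of PEA need onset time, which Protocol 6.3.1.3 lists as collected, or, if only dates are held, a blinded before/after-surgery flag. Events with a missing start day in the month of PEA need their own rule: SAP 13.4 sets the day to 01 when that month is later than the month of first dose, which would usually place them before surgery.

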9.1.2. Relationship of Adverse Events to Study Drug

The relationship or association of the study drug in causing or contributing to the AE will be characterised using the following classification and criteria:

Unrelated: This relationship suggests that there is no association between the study drug and the reported event.

Possible: This relationship suggests that treatment with the study drug caused or contributed to the AE, ie, the event follows a reasonable temporal sequence from the time of drug administration or follows a known response pattern to the study drug, but could also have been produced by other factors.

Probable: This relationship suggests that a reasonable temporal sequence of the event with drug administration exists and, based upon the known pharmacological action of the drug, known or previously reported adverse reactions to the drug or class of drugs, or judgment based on the investigator's clinical experience, the association of the event with the study drug seems likely. The event disappears or decreases on cessation or reduction of the dose of study drug.

Definite: This relationship suggests that a definite causal relationship exists between drug administration and the AE, and other conditions (concurrent illness, progression/expression of disease state, or concurrent medication reaction) do not appear to explain the event. The event reappears or worsens if the study drug is readministered.

Treatment-related AEs are those rated by the investigator as "definite," "probable," or "possible." In case the relationship is unknown or missing, the worst case (definite) will be assumed and the AE will be considered to be drug related. TEAEs will be summarised by SOC, PT and relationship using the frequency counts and percentages.

The above analysis will also be conducted for TEAEs occurred from V0 to V3 for overall patients in the Safety set and by subgroups as defined in section 4.4.

9.1.3. Severity of Adverse Event

The severity, or intensity, of an AE refers to the extent to which an AE affects the patient's daily activities. The intensity of the AE will be rated as mild, moderate, or severe using the following criteria:

Mild: An event usually transient in nature and generally not interfering with normal activities.

Moderate: An AE that is sufficiently discomforting to interfere with normal activities.

Severe: An AE that is incapacitating and prevents normal activities.

In case the severity is unknown or missing, the worst case (severe) will be assumed in the summary tables. A summary of TEAEs by SOC, PT and severity will be performed using the worst severity grade.

The above analysis will also be conducted for TEAEs occurred from V0 to V3 for overall patients in the Safety set and by subgroups as defined in section 4.4.

9.1.4. Serious Adverse Events

A serious adverse event (SAE) is defined as any event that results in death, is immediately life threatening, requires inpatient hospitalisation or prolongation of existing hospitalisation, results in persistent or significant disability/incapacity, or is a congenital anomaly/birth defect. The

hospitalisation due to study-related procedures ie, for scheduled RHC and PEA will not be considered as an SAE for this study.

The serious TEAEs, treatment-related serious TEAEs will be summarised by SOC and PT using the frequency counts and percentages. All serious AEs will be presented in a listing.

The above analysis will also be conducted for TEAEs occurred from V0 to V3 for overall patients in the Safety set and by subgroups as defined in section 4.4.

9.1.5. TEAEs Leading to Treatment Discontinuation/Study Discontinuation

TEAEs leading to permanent discontinuation of treatment and TEAEs leading to study discontinuation will be summarised by SOC and PT using the frequency counts and percentages respectively.

The above analysis will also be conducted for TEAEs occurred from V0 to V3 for overall patients in the Safety set and by subgroups as defined in section 4.4.

9.1.6. TEAEs Leading to Death

TEAEs with outcome death will be summarised by SOC and PT using the frequency counts and percentages.

All-cause of death during the whole study course will be presented in a listing.

The above analysis will also be conducted for TEAEs occurred from V0 to V3 for overall patients in the Safety set and by subgroups as defined in section 4.4.

9.1.7. TEAEs of Special Interest

The following TEAEs of special interest will be defined and included in summary tables by treatment group:

MedDRA coding

- “Myocardial infarction” and “Acute myocardial infarction” as preferred term;
- “Haemorrhage” will be assessed by using the standardised MedDRA query (SMQ);
- “Hypotension”, “haemoptysis”, “syncope” will be assessed as preferred term;
- “Stroke” will be assessed by using the preferred terms “haemorrhagic stroke”, “ischaemic stroke” and “embolic stroke”.

The TEAEs of special interest will be summarized by group: Myocardial infarction, Haemorrhage, Hypotension, Haemoptysis, Syncope, Stroke and also by study period V0 to V2, V0 to V4, medication of interest subgroup as defined in Section 4.4. The number of patients along with number of events in each level of summary will be provided.

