The efficacy measures include reduction in PVR, cardiac index, mean right atrial pressure, mean pulmonary arterial pressure, pulmonary artery wedge pressure, number and cause of deaths during the study, pulmonary hypertension-related hospitalisation, need for PAH-targeted and other medications, change in World Health Organization functional class for PAH, perioperative findings that include circulatory arrest time and surgery-related complications, surgical evaluation of specimen, withdrawal during the treatment phase, N-terminal pro-B-type natriuretic peptide, length of hospital and intensive care unit stay, and time on mechanical ventilation.

Safety Assessments:	Safety assessments include monitoring of adverse events, vital sign measurements, electrocardiogram measurements, physical examinations, clinical laboratory examinations, and pregnancy testing.
Study Drug, Dosage, and Route of Administration:	
Patients will initiate the treatment with either riociguat 1 mg or matching placebo tablets tid orally for 3 months. The study drug will be initiated no later than 180 days after RHC (used for screening of patients) and within 90 days of planned RHC before PEA.
 
The dose can be increased by 0.5 mg at 2-week intervals based on the tolerability (SBP) up to a maximum dose of 2.5 mg tid.
 
The individual study drug dose of the next titration step will be determined every 2 weeks at home according to the peripheral SBP measured at trough before intake of the morning dose under consideration of the following algorithm:
 
• If trough SBP \geq95 mmHg, increase dose (+0.5 mg tid)• If trough SBP <95 mmHg without symptoms of hypotension, maintain the dose• If any SBP <95 mmHg with clinical symptoms of hypotension such as dizziness or presyncope, stop study drug; restart after 24 hours with reduced dose (-0.5 mg tid) 
The BP measuring device will be supplied along with study drug to each patient to monitor BP at home. If the dose is interrupted for 3 or more days, restart the dose with 1 mg tid and follow the up-titration algorithm. The up-titration will be monitored by study staff contacting the patient by telephone at home.

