5.2 Treatments Administered

Patients will initiate the treatment with either riociguat or matching placebo tablets orally tid for 3 months. The study drug will be initiated no later than 180 days after RHC (used for screening of patients) and within 90 days of planned RHC before PEA. Right heart catheterisation will be performed within 3 months of the initiation of treatment per site procedures no more than 1 week prior to PEA. The study drug will be initiated at 1 mg and the dosage can be increased by 0.5 mg at 2-week intervals based on tolerability (SBP) up to a maximum dose of 2.5 mg tid. The individual study drug dose of the next titration step will be determined every 2 weeks at home according to the peripheral SBP measured at trough before intake of the morning dose under consideration of the following algorithm:

- If trough SBP \geq 95 mmHg, increase dose (+0.5 mg tid)
- If trough SBP $<$ 95 mmHg without symptoms of hypotension, maintain dose
- If any SBP $<$ 95 mmHg with clinical symptoms of hypotension such as dizziness or presyncope, stop study drug; restart after 24 hours with reduced dose (-0.5 mg tid)

The BP measuring device will be supplied along with study drug to each patient to monitor BP at home. If the dose is interrupted for 3 or more days, restart the dose with 1 mg tid and follow the up-titration algorithm. The up titration will be monitored by study staff contacting the patient by telephone at home.

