6.3.1.7 Adverse events of special interest

Adverse events of special interest will be separately analysed and closely monitored throughout the course of the study for safety reasons.

Adverse events of special interests are defined as myocardial infarction, haemorrhage, hypotension, haemoptysis, syncope and stroke.

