3.4. Dose Adjustment/Modifications

The study drug will be initiated at 1 mg and the dosage can be increased by 0.5 mg at 2-week intervals based on tolerability (SBP) up to a maximum dose of 2.5 mg tid. The individual study drug dose of the next titration step will be determined every 2 weeks at home according to the peripheral SBP measured at trough before intake of the morning dose under consideration of the following algorithm:

- If trough SBP \geq 95 mmHg, increase dose (+0.5 mg tid)
- If trough SBP <95 mmHg without symptoms of hypotension, maintain dose
- If any SBP <95 mmHg with clinical symptoms of hypotension such as dizziness or presyncope, stop study drug; restart after 24 hours with reduced dose (-0.5 mg tid)

The blood pressure (BP) measuring device will be supplied along with study drug to each patient to monitor BP at home. If the dose is interrupted for 3 or more days, restart the dose with 1 mg tid and follow the up-titration algorithm. The up titration will be monitored by study staff contacting the patient by telephone at home.

4. General Statistical Considerations

- Data from all study centers will be combined for analysis.
- Statistical methods to be used will be mainly descriptive. Summary statistics will be tabulated and represented graphically, whenever appropriate.
- Continuous data will be summarised using descriptive statistics (i.e. n, mean, standard deviation, median, minimum, and maximum). Besides presentation of absolute values, tabulation for differences to baseline by time will be provided, if appropriate. Categorical data will be summarised using the frequency counts and percentages. Time to event data will be analysed using the Kaplan-Meier method.

- For the summary statistics of all numerical variables, unless otherwise specified, minimum and maximum will be displayed to the same level of precision as reported. Mean and median will be displayed to one level of precision greater than the data collected. Standard deviation / standard error will be displayed to two levels of precision greater than the data collected. P-values will be rounded to three decimal places. If a p-value is less than 0.001 it will be reported as “<0.001”. If a p-value is greater than 0.999 it will be reported as “>0.999”.

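### The hypotension event of special interest rests on one preferred term, so symptomatic low-pressure episodes recorded by their symptom may be missing from its summary row

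*SAP*

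**What the plan says.** Protocol 6.3.1.7 sets the list: "Adverse events of special interests are defined as myocardial infarction, haemorrhage, hypotension, haemoptysis, syncope and stroke". It asks for these events to be analysed separately and watched closely. Amendment 2 (protocol 12.3.2.3) gives stronger safety monitoring as the reason for adding them.

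SAP 9.1.7 turns the list into search rules:

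- Myocardial infarction: two preferred terms.
- Haemorrhage: a standardised MedDRA query.
- Stroke: "will be assessed by using the preferred terms" for haemorrhagic, ischaemic and embolic stroke.
- Hypotension, haemoptysis and syncope: each "will be assessed as preferred term".

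The resulting groups are summarised by treatment arm, by study period (V0 to V2 and V0 to V4) and by the medication subgroups of SAP 4.4, which include β-blocker use.

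Separately, the titration algorithm in the protocol synopsis reads "If any SBP <95 mmHg with clinical symptoms of hypotension such as dizziness or presyncope, stop study drug", followed by a restart at a reduced dose. Protocol 5.2 and SAP 3.4 carry the same rule.

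**The concern.** Both documents name dizziness and presyncope as the symptoms that, with SBP below 95 mmHg, mark a hypotensive episode serious enough to interrupt study drug. Neither symptom is a term in the special-interest list. Titration takes place at home, with a patient-held device and telephone contact (protocol 5.2), and adverse events are elicited by a nonleading question (protocol 6.3.1.2). No text tells sites to record the diagnosis rather than the symptom. An episode that meets the trial's own trigger could therefore enter the database as dizziness, presyncope or a low blood-pressure finding.

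What is at stake is a prespecified safety count for the risk that governs titration. If it is incomplete, the subgroup and period tables built from it are incomplete too.

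**Working it through.** **1. The rules side by side.** Three of the six groups (myocardial infarction, stroke, haemorrhage) use more than one term. The SAP thus accepts that one medical concept may be spread over several codes, but does not apply this to hypotension.

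**2. Where a rule-triggered episode recorded as dizziness would appear.**

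- SAP 9.1.7, hypotension row: no.
- SAP 9.1.1 to 9.1.3, TEAEs by term, relationship and severity: yes, under dizziness, mixed with dizziness from other causes.
- SAP 9.1.5: no, because it covers only permanent treatment discontinuation and study discontinuation.
- SAP 7.2.1, exposure: only through average daily dose and maximum dose level; no table of reductions or temporary stops is planned.
- SAP 9.3, vital signs: summarised by scheduled visit; home readings are not mentioned.
- SAP 9.1 AE listing (action taken) and SAP 7.2 administration listing: yes, but as listings only.

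No planned table identifies the episode as hypotension.

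**3. Size, under an assumption.** Inputs: hypotension in 11 of 75 patients in Study 12166 (protocol 1.4), and 88 patients randomised 1:1, so 88 / 2 = 44 per arm. The check 11/75 = 14.7% agrees with the stated 15%. Protocol 1.4 reports that figure by MedDRA preferred term, so it is already the kind of count that SAP 9.1.7 will produce.

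Let u be the fraction of affected patients recorded by symptom only. Then reported = true × (1 − u), so true = reported / (1 − u). The documents give no value for u; one third, with a range of 10% to 50%, is an assumption.

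| u | True rate behind a reported 14.7% | Patients in 44, true v reported |
|---|---|---|
| 10% | 14.7 / 0.90 = 16.3% | 7.2 v 6.5 |
| one third | 14.7 / 0.667 = 22.0% | 9.7 v 6.5 |
| 50% | 14.7 / 0.50 = 29.3% | 12.9 v 6.5 |

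The row would miss about 1, 3 or 6 patients in the riociguat arm.

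**4. Effect on the comparison.** With equal u in both arms, the difference becomes (p1 − p0)(1 − u) and the ratio stays p1/p0. For illustration, assume true rates of 20% v 5% (neither is in the documents):

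| u | Reported rates | Difference | Ratio | Expected patients |
|---|---|---|---|---|
| 0 | 20.0% v 5.0% | 15.0 points | 4 | 8.8 v 2.2 |
| 10% | 18.0% v 4.5% | 13.5 points | 4 | 7.9 v 2.0 |
| one third | 13.3% v 3.3% | 10.0 points | 4 | 5.9 v 1.5 |
| 50% | 10.0% v 2.5% | 7.5 points | 4 | 4.4 v 1.1 |

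**The case against.** **The events are not lost.** A reader might infer that symptom-coded episodes go uncounted. They do not: SAP 9.1.1 tabulates every TEAE by term and arm, SAP 9.1 lists all AEs with action taken, and syncope has its own special-interest group. This stands, and it confines the point to one row and its subgroups. It does not remove the point, because the general dizziness row mixes causes and the hypotension count cannot be recovered from it.

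**Sites may well record hypotension.** Staff who apply the titration rule have a measured SBP, and the rule itself calls the symptoms those of hypotension. Protocol 6.3.6 also has clinically significant vital-sign abnormalities recorded as AEs. So it would be too strong to say that episodes will be coded to the symptom; they may be. Protocol 6.3.6 does not settle it either, since a low reading entered as such may be coded to a term other than Hypotension.

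**Background rates do not give the loss.** It is tempting to say that a true 15% would be reported as 10%. That runs the wrong way, because the 15% is already a preferred-term count. It is also tempting to treat the pooled dizziness rates of 19% v 12% (44 × 0.19 = 8.4 and 44 × 0.12 = 5.3 patients) as missed hypotension. Those rates cover dizziness in general, and the documents do not say what share accompanied SBP below 95 mmHg.

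**Main risk is not the documents' term.** The most frequent excess AEs named in the pooled pivotal studies are headache, dizziness and dyspepsia. The text supports calling hypotension the risk that governs titration, and no more.

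**Nothing formal hangs on the row.** No between-arm test is planned for special-interest events, and protocol section 7 calls all analyses exploratory. The SAP also follows the protocol list literally. All of this is true and limits the weight of the point, but a descriptive safety count should still capture what it is named for.

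**Conclusion.** The point holds as a cheap improvement to a prespecified safety summary. The single-term rule is narrower than the rules for three other events in the same section, and it does not match the symptomatic episode described in protocol 5.2 and SAP 3.4. Following it can understate hypotension in the special-interest row and in the tables by period and medication.

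The size of any undercount cannot be derived from the documents. On the assumption that one third of affected patients are recorded by symptom only (range 10% to 50%), a reported rate near 15% would stand for a true rate of about 22% (16% to 29%). The difference between arms would shrink by the same fraction. The ratio would be unchanged only if capture is equal in both arms, which is also an assumption.

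**What to change.** Before unblinding, add to SAP 9.1.7 a grouped hypotension definition with medical sign-off, made up of:

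1. the preferred term Hypotension;
2. a fixed list of other preferred terms for low or falling blood pressure;
3. dizziness or presyncope AEs whose recorded action taken was interruption or reduction of study drug, or which have an SBP below 95 mmHg where that reading is in the database.

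Report the grouped count beside the single-term count, by arm and in the same period and medication tables.

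The cost is SAP wording, a term list and some programming. Action taken with study drug is already collected (protocol 6.3.1.3), so that part needs no new data. The SBP part depends on whether home readings reach the eCRF. The documents do not say, and the sponsor should confirm; if they do not, drop that part and say so. The downside is a slightly higher and somewhat less specific rate, since some dizziness with a dose change will have another cause. The dosing rule stays as it is.
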